#### 8.1.1 *Definition of an Adverse Event*

An AE is the development of an undesirable medical condition or the deterioration of a pre-existing medical condition following or during exposure to a pharmaceutical product, whether or not considered causally related to the product. An undesirable medical condition refers to symptoms (e.g. nausea, chest pain), signs (e.g. tachycardia, enlarged liver) or the abnormal results of an investigation (e.g. laboratory findings, ECG). In clinical studies, an AE can include an undesirable medical condition occurring at any time, including run in or washout periods, even if no IMP has been administered.

This definition includes events occurring from the time of the subject giving informed consent until the end of the study treatment (as defined in [Section 3.6](#) and [Section 5.6](#)).

Natural progression or deterioration of the locally advanced or metastatic RCC with a clear-cell component under study will be recorded as part of the efficacy evaluation and should not be recorded as an AE/SAE.

Death due to disease progression will be recorded as part of the efficacy evaluation and will not be regarded as an SAE.

Signs and symptoms should not be reported as AEs/SAEs if they are clearly related to a relapse or an expected change or progression of the clear-cell component RCC.

These signs and symptoms should only be reported as AEs/SAEs (depending on the Investigator's judgement) if they are:

- Judged by the Investigator to be unusually severe or accelerated clear-cell component RCC, or
- If the Investigator considers the deterioration of clear-cell component RCC signs and symptoms to be caused directly by the IMP.

If there is any uncertainty about an AE being due solely to clear-cell component RCC, it should be reported as an AE/SAE as appropriate.

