### ***8.1.3 Recording and Follow-up of Adverse Events***

All observed or self-reported AEs, regardless of suspected causal relationship to IMP, will be recorded on the AE page(s) of the eCRF. Events involving drug reactions, accidents, illnesses

with onset during the treatment phase of the study or exacerbations of pre-existing illnesses should be recorded according to the NCI terminology.

Any AEs already recorded and designated as 'continuing' should be reviewed at each subsequent assessment.

For all AEs, the Investigator must pursue and obtain adequate information both to determine the outcome of the AE and to assess whether it meets the criteria for classification as an SAE requiring immediate notification of the Sponsor or its designated representative. For all AEs, sufficient information should be obtained by the Investigator to determine the causality of the AE (i.e. treatment with cabozantinib or other illness). The Investigator is required to assess causality and record that assessment on the eCRF. Causality assessment of AEs should include at minimum confounding factors such as disease and concomitant medications.

Follow-up of the AE after the date of cabozantinib discontinuation is required until the event or its sequelae resolve or stabilise at a level acceptable to the Investigator and the Sponsor's clinical monitor or his/her designated representative.

During the follow-up period, any SAE that occur more than 30 days after the date of the last cabozantinib dose, assessed as related to study treatment or study procedures will also be collected and followed until resolution or stability according to the Investigator.

Follow-up of SAEs/ Grade 3 and 4 AEs leading to study treatment discontinuation:

All SAEs that are ongoing at 30 days or later after the date of the last dose of study treatment and AEs assessed NCI-CTCAE Grade 3 or 4 that led to study treatment discontinuation that are ongoing 30 days after the last dose of study treatment are to be followed until either:

- the AE has resolved;
- the AE has improved to Grade 2 or lower;
- the Investigator determines that the event has become stable or irreversible;

The status of all other AEs that are ongoing 30 days after the last dose will be documented as of the last study visit for the subject.

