1.3.2.2 Safety assessments

The timing of safety assessments is provided in [Table 2](#).

The safety endpoints are detailed in [Section 3.1.3](#), and the statistical methods to be used in the analysis of these safety endpoints are provided in [Section 3.2.2](#).

Adverse Events

Adverse events (AEs) will be monitored from the time the subject gives informed consent and throughout the study treatment (see [Section 1.2.2](#) for a definition of study

SAP Final: Version 6.0: 17 August 2023

duration) and will be assessed by direct, nonleading questioning. All adverse events are to be reported during the treatment period, which includes 30 days after the date of the last cabozantinib dose. During the follow-up period, any SAEs that occur more than 30 days after the date of the last cabozantinib dose, assessed as related to cabozantinib or study procedures will also be collected and followed until resolution or stability according to the Investigator. In case of screen failure, AEs will be recorded until the date the subject is deemed to be a screen failure.

Adverse events will be recorded and graded according to the National Cancer Institute for Adverse Events (NCI-CTCAE) version 5.0.

The relationship of an AE to investigational medicinal product (IMP) administration will be classified into Related or Not Related.

Abnormalities in laboratory test values should only be reported as AEs if any of the following apply:

- They result in a change in IMP schedule of administration (change in dosage, delay in administration, IMP discontinuation);
- They require intervention or a diagnosis evaluation to assess the risk to the subject;
- They are considered as clinically significant by the Investigator.

Clinically significant changes, in the judgement of the Investigator, in physical examination findings (abnormalities) will be recorded as AEs.

Any other abnormal test findings judged by the Investigator as clinically significant (e.g. electrocardiogram [ECG] changes, thyroid function disturbances) that result in a change in study drug dosage or administration schedule, or in the discontinuation of the study drug, or require intervention or diagnostic evaluation to assess the risk to the subject, should also be recorded as AEs.

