All AEs will be coded according to the most recent version of the Medical Dictionary for Regulatory Activities (MedDRA) and will be classified by PT and SOC. AEs will be graded according to the NCI-CTCAE version 5.0.

Adverse event listings (Listings 16.2.7.1 to 16.2.7.9) will be presented by cohort, subject id, SOC and PT. Listings of serious adverse events (SAEs), adverse events leading to withdrawal and listings of deaths will also be presented. Treatment-emergent AEs (TEAEs) will be flagged (*) in the AEs listings and will be summarized.

A TEAE is defined as any AE that occurs after first dose of study drug if:

- it was not present prior to receiving the first dose of study drug, or
- it was present prior to receiving the first dose of study drug but the intensity increased during the active phase of the study.

The focus of analysis for this study will be the duration of the treatment period and 30 days after the date of last study drug administration.

If AE start and/or stop dates are missing or partial, the rules mentioned in Section 3.2.3.2 will be applied, and the algorithm for imputation is defined in Appendix 1 (10).

SAP Final: Version 6.0: 17 August 2023

A summary table of overall counts will include the number of subjects with: any AE, any TEAE, any TEAE of Grade 3 or 4, any study drug related TEAE, any study drug related TEAE of Grade 3 or 4, any serious TEAE, any study drug related serious TEAE, any TEAE leading to study drug withdrawal, any TEAE leading to study drug interruption, any TEAE leading to a dose reduced, any TEAE leading to death (Table 14.3.1.1). TEAEs associated with change of schedule of administration will be defined as those with an action taken with study drug as dose reduced or study drug interrupted.

The incidence of all TEAEs will be tabulated by cohort and overall, with the number and percentage of subjects with adverse events classified by SOC (ordered alphabetically) and PT (in descending order of overall PT incidence) (Table 14.3.1.2). The number of occurrences of a TEAE will also be presented. Summary of TEAEs with incidence rate above or equal 10% will also be presented (Table 14.3.1.3).

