For TTR, DOR, PFS and OS, the imputation rules in case of partial dates are defined in Appendix 1 (2), (3), (4) and (5), respectively.

The most conservative approach will be systematically considered (i.e. if the onset date of an AE/concomitant medication is missing / incomplete, it is assumed to have occurred during the study treatment phase [i.e. a TEAE for AEs] except if the partial onset date or other data [stop date, ...] indicates differently).

A missing/incomplete date of medical history or disease diagnosis will be assumed to have occurred before any study treatment.

If a partial date and the associated information do not allow to state about the assignation to a group / category, all the possible groups / categories will be considered (i.e.: an AE could be assigned to several possible doses at event onset according to its partial onset date and stop date. Particularly an AE with missing start date will be assigned to each dose received before its end date. Similarly, a medication with partial start and stop dates could be considered as prior and concomitant treatment).

Where this is possible, the derivations based on a partial date will be presented as superior inequalities (i.e.: for an AE started in APR2004 after the administration performed on 31MAR2004, the days since last dose will be “ ≥ 2 ”, similarly the duration of ongoing AEs or medication will be “ $\geq xx$ ” according to the start and last visit dates.).

For TEAE flag, the algorithm is defined in Appendix 1 (10) in case of partial start or stop dates. For time from first dose for adverse events, the imputation rules in case of partial dates are defined in Appendix 1 (11).

For prior/concomitant medication flag, the algorithm is defined in Appendix 1 (16) in case of partial start or stop dates.

For time from diagnosis to screening, the imputation rules in case of partial dates are defined in Appendix 1 (17).

For treatment duration on 1st anti-cancer therapy for subgroup analysis (see Section 3.2.16), the imputation rules in case of partial dates are defined in Appendix 1 (18). In case, the duration treatment cannot be derived as <6 months, or ≥ 6 months based on the available data, the subgroup ≥ 6 months will be considered by default.

3.2.4 *Subject disposition*

Listings of treatment batch number and of enrolment scheme and codes will be presented by subject for each cohort (Listings 16.1.6 and 16.1.7).

SAP Final: Version 6.0: 17 August 2023

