Following the Functional Assessment of Cancer Therapy – Kidney Symptom Index – Disease Related Symptoms (Fksi-DRS) Scoring Guidelines Version 4 [4], the 9 item answers will be coded as: “Not at all” = 0, “A little bit” = 1, “Some-what” = 2, “Quite a bit” = 3, and “Very much” = 4.

When at least 50% of items (i.e. 5 items) were answered in the subject questionnaire, the Fksi-DRS Total Score will be calculated as follows.

First, each item will be reversed by doing 4 minus the answer. Then, these individual reversed items will be summed to obtain a score. In last step, this score will be prorated by multiplying by the total number of items in the subscale (i.e. 9) and by dividing by the number of items answered in the questionnaire. This will produce the symptom index score.

The score ranges from a minimum possible score of 0 to a maximum possible score of 36.

As with all FACIT questionnaires, a high score is good. Therefore, a score of “0” is a severely symptomatic subject and the highest possible score is an asymptomatic subject.

(7) Changes from Baseline

Changes from Baseline will be calculated as a difference from Baseline (e.g. assessment at the visit – assessment at Baseline).

(8) Percent change from Baseline

Percent change from Baseline will be calculated as a percentage of change from Baseline (e.g. $100*((\text{assessment at the visit} - \text{assessment at Baseline}) / (\text{assessment at Baseline}))$).

(9) Percent change from nadir

Nadir is the smallest sum of measurements at prior timepoints (including baseline). Percent change from nadir will be calculated as a percentage of change from nadir (e.g. $100*((\text{assessment at the visit} - \text{assessment at nadir}) / (\text{assessment at nadir}))$).

(10) Algorithm for TEAE flag

An AE will be classified as a TEAE in case AE start date is between the first dose of study drug and the last study drug administration plus 30 days.

In case of an incomplete AE start date, an AE start date imputation algorithm will be implemented as described in the Table below. Classification of adverse event according to its treatment-emergent status is then performed using the imputed date.

In the following table, all dates are presented using an YYYY-MM-DD format. As an example, suppose first dose of study drug is equal to 2002-08-11 and several AEs have incomplete start dates.

SAP Final: Version 6.0: 17 August 2023

| Description of incomplete AE start date | Imputed numeric date | Example | |

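### The SAP's treatment-emergent flag tests only the AE start date and omits the worsening limb of the SAP's and protocol's own TEAE definition

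*SAP*

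**What the plan says.** SAP Section 3.2.2.1 (Adverse events) and Protocol Section 11.4.4 give the same definition with two limbs. An AE occurring after the first dose is treatment-emergent if it was absent before that dose, or if "it was present prior to receiving the first dose of study drug but the intensity increased during the active phase of the study".

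SAP Appendix 1 (10), titled as the algorithm for the TEAE flag, opens with a general rule: "An AE will be classified as a TEAE in case AE start date is between the first dose of study drug" and the last administration plus 30 days. It then gives a table for imputing incomplete start dates and adds: "Classification of adverse event according to its treatment-emergent status is then performed using the imputed date". Neither the opening rule nor the table uses intensity.

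SAP Section 3.2.3.2 points to this appendix item for incomplete dates: "For TEAE flag, the algorithm is defined in Appendix 1 (10) in case of partial start or stop dates".

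On collection, SAP Section 1.3.2.2 says: "Adverse events (AEs) will be monitored from the time the subject gives informed consent". For events already on record, Protocol Section 8.1.3 says: "Any AEs already recorded and designated as 'continuing' should be reviewed at each subsequent assessment". SAP Section 5, which lists departures from the protocol, mentions no change to the TEAE definition.

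**The concern.** The definition and the rule that a programmer would code do not agree. The date rule delivers the first limb and drops the second. AEs are collected from consent, so some records can start before the first dose, and these are the records on which the second limb operates.

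The flag feeds most of the safety output: the TEAE incidence tables, Grade 3 or 4 events, related events, events leading to withdrawal, interruption, dose reduction or death, and the Kaplan-Meier analysis of time to a first Grade 3 or 4 TEAE. In Appendix 3 the main serious-event tables (14.3.2.1 to 14.3.2.3) are also titled as treatment-emergent. Any misclassification from the missing limb goes one way, towards fewer TEAEs, whereas the SAP takes the conservative direction for missing AE dates.

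**Working it through.** No sample size, power or event count is involved. The check applies both rules to the same cases.

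**Inputs.** The first dose is 2002-08-11, from the worked example in SAP Appendix 1 (10). The last dose is set at 2003-02-11, which is an assumption that does not affect the result. Last dose plus 30 days is then 2003-03-13.

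**Rules.**
- Appendix 1 (10): flag if first dose ≤ start date ≤ last dose + 30 days.
- Section 3.2.2.1: flag if start date ≥ first dose, or if start date < first dose and intensity increased on treatment.

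**The SAP's own imputation table, with AE end date missing.**
- 2002-07-XX becomes 2002-07-01: not flagged.
- 2002-08-XX becomes 2002-08-11: flagged.
- 2002-09-XX becomes 2002-09-01: flagged.
- 2001-XX-XX becomes 2001-01-01: not flagged.
- 2002-XX-XX becomes 2002-08-11: flagged.
- 2003-XX-XX becomes 2003-01-01: flagged.
- Fully missing becomes 2002-08-11: flagged.

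The table reproduces, apart from a misprint: the example column shows 2022-08-11 where the example's first dose is 2002-08-11.

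**Four complete-date cases.**

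| Start date | Worsened on drug | Appendix 1 (10) | Section 3.2.2.1 |
|---|---|---|---|
| 2002-08-01 | No | Not TEAE | Not TEAE |
| 2002-08-01 | Yes | Not TEAE | TEAE |
| 2002-08-20 | No | TEAE | TEAE |
| 2002-08-20 | Yes | TEAE | TEAE |

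The rules disagree only in the second row: start before first dose, intensity increased on drug. The same happens with a partial date. A start of 2002-07-XX is imputed to 2002-07-01 and stays unflagged even if the event worsened on drug, while Section 3.2.2.1 counts it.

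**After adding the intensity condition.** The second row changes to TEAE and the other three rows stay as they are, so the two rules then agree on all four cases.

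**Can the case arise?** Yes, in a limited window. Collection starts at consent, and Protocol Section 5.2.1 allows consent more than 15 days before screening. However, screening and baseline may fall on the same day (Protocol Table 2, footnote a), so for some subjects the window is close to nil.

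**The case against.** The strongest reply is that Appendix 1 (10) handles dates and does not redefine a TEAE. Sections 3.2.2.1 and 3.2.3.2 send the reader there for missing or partial dates, the two-limb definition stands in the main text and matches the protocol, and Section 5 declares no change. This has some force, since an attentive programmer could treat Section 3.2.2.1 as governing. It does not remove the conflict. The opening sentence of Appendix 1 (10) is not restricted to incomplete dates; the paragraph on incomplete dates comes after it. Even on the narrow reading, the worsening limb is lost for partial start dates before the month of first dose.

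The second reply is that worsening may already be captured as a new event. Protocol Section 8.1.1 says: "An AE is the development of an undesirable medical condition or the deterioration of a pre-existing medical condition". Section 8.1.3 asks for exacerbations of pre-existing illness to be recorded, and Table 2 refers to collecting new or worsening AEs. If each worsening gets its own record and date, the start-date rule catches it. This is plausible, particularly for medical-history conditions, and it stands as a limit on the point. But neither document says how a grade rise in an AE already on record is dated. The protocol mentions eCRF completion guidelines, which might settle it, but they are not part of the documents.

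Third, the reach is limited. A subject with any other TEAE still counts in overall incidence, so the effect would fall mainly on preferred-term, grade and action-taken rows. The any-AE overview row, the all-AE listing, the death-form summary and the laboratory grade shifts do not depend on the flag. This is also correct.

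**Conclusion.** The inconsistency is real. SAP Appendix 1 (10), followed as written, fails to flag an AE that starts between consent and first dose and then worsens on drug, although the SAP and protocol definitions both count it. Whether any event is lost depends on an unstated matter: whether sites enter such a worsening as a separate record with an on-treatment start date. If they always do, the loss is zero.

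Two stronger readings are tempting and are not supported. A reader might infer that continuing AEs remain on their original record under the original start date, so that reported TEAE counts are certain to be too low. Protocol Section 8.1.3 requires only that such events be reviewed; it is silent on how a grade change is entered. A reader might also want to put a number of patients on the undercount. The documents give no rate of pre-dose AEs and no rate of worsening, so any figure would be a guess.

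The point concerns safety reporting only. The objective response rate analysis does not use the flag.

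**What to change.** Add to SAP Appendix 1 (10) that an AE starting before the first dose is also a TEAE if its CTCAE grade increased between the first dose and the last dose plus 30 days. Keep the condition to intensity, because the definition refers to nothing else; adding other criteria such as seriousness would widen it.

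This requires dated grade changes. If the eCRF holds only one grade per AE record, state instead that each worsening is a separate AE record dated at the grade increase, so that the existing start-date rule captures it. Because SAP version 6.0 is dated 17 August 2023 and inclusion was planned to stop by 30 June 2022, this route would also need a check that AEs with pre-dose onset were entered that way. In either case, cross-refer Appendix 1 (10) to the definition in Section 3.2.2.1, and correct the 2022-08-11 misprint at the same time.

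The cost is minor programming and data checking.
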